After determination of motor threshold, the TMS coil will be positioned at predetermined locations over the cortex using frameless stereotaxy as described above. Surface electrodes will be kept over hand muscles on both hands for the purpose of continuous monitoring of the safety of the procedure. We will also use theta bursting TMS (TBS) at inhibitory settings (continuous TBS-cTBS).

Theta burst TMS will be limited to established protocols using 600 pulses per session (40 seconds for cTBS). The first TMS session could last as short as 2 hours and as long as 3 hours with multiple sessions of TBS administered with a break of 30-minutes in between sessions.

Daily rTMS sessions (for MdDS subjects only)

Participants with MdDS will receive one sessions each of 3 different targets: occipital cortex, cerebellar vermis, lateral cerebellar hemisphere. The order in which these sessions will be administered will be randomized between participants. All test sessions will be done on Day 2 (Day 1 will involve baseline fMRI and EEG measurements). The treatment choice will depend a combination of the participant's assessment of which target was a the most effective in reducing the vertigo. If they are not sure, then balance assessment with the SWAY balance app will be used to determine which protocol improved their balance the most.

We plan an enrollment of 24 participants which would provide 4 groups of each of 6 possible orders of stimulation. Participants will be asked to rate the intensity of their rocking vertigo. The goal is to provide up to 12 sessions of rTMS over 3 days with 30-minutes of break in between. The end of the final day of stimulation will include fMRI and EEG.

E. Statistical Methods

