This is a pilot study so there are no set power calculations. The goal is to determine which if any of three rTMS targets are most effective in reducing oscillating vertigo. Pre-stimulation baseline scores will include weekly assessments of the DHI, MBRS, and the HADS divided into the Anxiety and Depression subscores. The median of 4 weekly prestimulation scores will be used as the baseline. The participants will be making immediate post assessments of each of these scores and weekly thereafter for 6 weeks. The differences between these weekly scores and the prestimulation baseline will be calculated. Baseline clinical features that determine target selection will be placed in a one-way ANOVA with one factor and three levels for response groups (occipital target, vermis target, lateral cerebellar target) with post hoc Bonferroni correction to determine which targets showed different responses.

F. Gender/Minority/Pediatric Inclusion for Research

Women and minorities will be included in the study. Prior research indicates that MdDS predominantly affects females, without any predilection for any racial or ethnic groups. It is a disorder of adults, however, as the average age of a first episode is near 40 years old.

G. Human Participants

We plan to enroll 24 subjects with MdDS and 20 healthy controls over a span of 5 years.

Inclusion criteria for controls:

1. Age \geq 18 years old
2. Willing and capable of interacting with the informed consent process
3. No history of dizziness or balance disorder.

Inclusion criteria for MdDS subjects:

1. Age \geq 18 years old
2. Willing and capable of interacting with the informed consent process
3. Primary disorder being a persistent perception of motion with no other cause determined after a careful interview.

Exclusion criteria for both:

1. Subjects who cannot comply with study conditions.
2. Active psychiatric condition such as mania or psychosis
3. Unstable medical condition
4. Implanted metal anywhere in the body (infusion pumps, pacemakers, metal or shrapnel in the body, deep brain stimulators, aneurysm clips, metal prostheses, joints, rods or plates). Dental fillings are acceptable.

5. Personal history of seizures or a first-degree relative with uncontrolled epilepsy

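### The plan asks which of three targets works best, but its only named test compares baseline features between self-selected groups, and the randomised Day 2 comparison has no analysis

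*Combined protocol and SAP*

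**What the plan says.** Section E (Statistical Methods) states the aim: "The goal is to determine which if any of three rTMS targets are most effective in reducing oscillating vertigo".

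Section D (Daily rTMS sessions) gives each MdDS participant one session at each of the three targets, all on Day 2. On sequence it says "The order in which these sessions will be administered will be randomized between participants", and on size "We plan an enrollment of 24 participants which would provide 4 groups of each of 6 possible orders of stimulation". The target for the treatment course is then picked from the participant's "assessment of which target was a the most effective in reducing the vertigo". For those who are unsure, the SWAY balance app is used "to determine which protocol improved their balance the most". Participants are also to rate their rocking vertigo, but no scale or timing is given there.

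Section E lists DHI, MBRS and the HADS subscores as outcomes, before stimulation and for 6 weeks after. Of these it says "The differences between these weekly scores and the prestimulation baseline will be calculated", with no clear test attached. The only named test is "Baseline clinical features that determine target selection will be placed in a one-way ANOVA with one factor and three levels for response groups", the three levels being the three targets, "with post hoc Bonferroni correction to determine which targets showed different responses".

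**The concern.** The design and the analysis do not meet. Section D sets up a three-period crossover that can compare the acute effects of the targets within each person. Section E does not analyse it: target, period, order and carryover appear in no model, and the rocking-vertigo rating is not among its outcomes.

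The test that is named has baseline features as its dependent variable and, on the most natural reading, the chosen target as its factor. It can show whether people who chose different targets differed beforehand. It cannot show whether targets differed in response, which is the purpose the same sentence gives it. Substituting follow-up change does not rescue it, because people enter a group according to how they responded on Day 2.

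At stake is the study's only stated analytic goal. A difference between chosen-target groups, or the lack of one, could be reported as evidence about target efficacy when it is neither. And if vertigo is not rated around each Day 2 session, the comparison that could have answered the acute question may not be recoverable.

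**Working it through.** **1. The plan's own figure.** Three targets can be ordered in 3! = 6 ways, and 6 x 4 = 24, so the planned enrolment reproduces. It comes from balancing orders. No power, alpha, effect size or variance is stated, so nothing else can be reproduced, and every effect and variance below is assumed.

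**2. Literal reading.** The F statistic is the between-group over the within-group mean square of a baseline feature. Neither term contains a response. With true mean improvements of 15/10/5 on a 0-100 rating, n = 24 and a feature unrelated to benefit, it rejects in 4.9-5.1% of 20,000 simulated trials per setting. That is the chance rate and follows by construction. If the feature is related to choice, rejection identifies a predictor of choice, still not a difference in efficacy.

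**3. Follow-up reading.** Let the benefit of target t in person i be mean(t) + person(i) + interaction(i,t). The person chooses the target with the best Day 2 response (benefit plus noise). Follow-up change is the benefit of the chosen target plus fresh noise. The group mean among choosers of t is then

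mean(t) + E[interaction(i,t) given that t was chosen].

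The common person effect cancels in the choice. The second term is the selection bias, and it differs by target.

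Results for true 15/10/5, a gap of 15 - 5 = 10:

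| Person-by-target SD | Noise SD | Common person SD | Chooser means | Gap |
|---|---|---|---|---|
| 10 for all | 5 | 0 | 20.2 / 17.8 / 15.4 | 4.8 |
| 15 for all | 10 | 0 | 23.4 / 20.7 / 18.0 | 5.4 |
| 10 for all | 10 | 10 | 19.5 / 16.1 / 12.7 | 6.8 |
| 5 for all | 5 | 10 | 16.6 / 13.2 / 9.8 | 6.8 |
| 15 / 10 / 5 | 5 | 0 | 24.1 / 17.0 / 8.2 | 15.9 |
| 5 / 10 / 15 | 5 | 0 | 16.6 / 18.9 / 22.4 | -5.8 |

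With all true means equal at 10, the follow-up ANOVA rejects in 4.8-4.9% of trials when the SDs are equal. When they are not, it rejects in 10.6% (SDs 12/10/8), 14.9% (15/10/10), 38.8% (5/10/15) and 56.4% (15/5/5).

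**4. Within-participant Day 2 contrast.** The model has target, period, pre-session rating and participant (fitted here as fixed effects), with baseline SD 15, noise split equally between pre and post ratings, and no common person effect.

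- The mean 15-versus-5 contrast is 10.0 in all four equal-SD settings and both unequal-SD settings.
- With equal means and SDs 15/5/5 it rejects in 6.4%.
- If half of the previous session's effect persisted, the contrast averages 8.4-8.6 without a carryover term and 10.0 with one.
- Least-squares contrast variance, in units of residual variance and without the covariate, is 2/24 = 0.0833, with 72 - 24 - 2 - 2 = 44 degrees of freedom. With first-order carryover it is 0.1042 on 42, and 0.1042/0.0833 = 1.25.

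**5. A second set of assumptions.** A separate simulation (10,000 runs; participant, participant-by-target and later-noise SDs all 1; no carryover) made one target better by 0, 0.5, 1.0 or 1.5 SD:

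| Analysis | 0 | 0.5 | 1.0 | 1.5 |
|---|---|---|---|---|
| Baseline feature by chosen target | 5.0% | 5.1% | 5.0% | 4.9% |
| Follow-up change by chosen target | 5.2% | 5.2% | 6.2% | 7.3% |
| Repeated-measures analysis of Day 2 | 4.8% | 39% | 94% | >99% |

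Day 2 responses and later change are different quantities, so these rows show what each analysis can detect. They are not a like-for-like power comparison.

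**The case against.** The best defence is that the ANOVA was meant as a search for predictors of target choice, which is how its opening words read. Section C supports this: handedness affected which side worked best in earlier work, and illness duration was related to benefit. On that reading the test is coherent and only its purpose clause is wrong. This stands as far as it goes, and the fix keeps the test for that use. But the stated goal is then left with no test at all.

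It is also fair that the follow-up reading is not what the sentence literally says, and that the large distortions need unequal variances which nothing in the documents supports. With equal SDs the ranking survives in all four settings and the null rejection rate is nominal. The figures are therefore illustration; the finding rests on the wording.

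Counts of chosen targets would be a simple pilot read-out. In a re-run of the equal-SD 15/10/5 settings, 45-63% chose the best target and 10-22% the worst. Section E does not plan these counts, and they give no effect size in rating units.

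A Visual Analogue Scale is listed among the enrolment questionnaires in Section D, and Section C describes a 0-100 version used before. Neither is linked to Day 2, so what is missing is that link and the timing.

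Finally, pilot status excuses the absence of a power calculation. It does not excuse a test that cannot address the stated goal.

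**Conclusion.** The concern holds, and the plan is wrong as written on this point. The only named test cannot support a statement about which target is most effective under either reading, and the randomised Day 2 comparison is left unanalysed. This follows from the text and needs no assumption about variances.

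The size of the distortion cannot be determined from the documents. Under the assumed settings, a true 10-point gap appears as anything from -5.8 to 15.9 among choosers, and false rejection under equal means ranges from about 5% to 56%.

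Two limits apply. The randomised order still protects each participant's choice from systematic order effects, although the named analysis makes no use of it. And Day 2 can speak only to acute single-session effects: for the treatment course there is no randomised comparison of targets, because the course target is selected after Day 2 testing. It must be fixed before analysis, and preferably before Day 2 data are collected.

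**What to change.** **In Section E:**

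- Make the acute target comparison a within-participant analysis of the rocking-vertigo rating after each Day 2 session. A suitable form is a linear mixed model with target and period as fixed effects, the pre-session rating as covariate and participant as random effect, with Bonferroni- or Holm-adjusted pairwise contrasts and confidence intervals. Paired differences with intervals would be an acceptable simpler choice for a pilot.
- Add a first-order carryover term as a sensitivity analysis. Sessions are 30 minutes apart, whereas the earlier acute comparison in Section C separated them by at least two days.
- Keep the one-way ANOVA only as an exploratory analysis of baseline predictors of target choice, and correct its stated purpose.
- Report how many participants chose each target, split by own judgement and SWAY.
- Report follow-up DHI, MBRS and HADS change by chosen target descriptively, without ranking targets.
- State that the Day 2 comparison concerns single-session acute effects, not the treatment course or the 6-week outcomes, and that the course has no randomised comparison of targets.

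**In Section D (Daily rTMS sessions):** name the rating scale and state that it is completed before and after each Day 2 session.

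**Cost:** one analysis paragraph, one sentence, and up to 3 x 2 = 6 short self-ratings per participant, or 6 x 24 = 144 in all. The carryover sensitivity model has about 25% more contrast variance. No stimulation setting, schedule or target-selection rule changes.
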